13 DATA AND SAFETY MONITORING

13.1 Data reporting

13.1.1 Method

Lumicell will collect, manage, and monitor data for this study.

13.1.2 Data submission

It is the expectation that all CRFs will be completed in a contemporaneous manner to the time of study related procedures. Timely completion of the reports will allow Lumicell to monitor the study conduct and data in an effective manner.

13.2 Safety review

A Medical Monitor will review and monitor adverse events data from this trial. The Medical Monitor will be a medical doctor with experience in oncology and who has no direct relationship with the study. Information that raises any questions about subject safety will be addressed with the Principal Investigator and study team.

13.3 Monitoring

Lumicell will conduct a study assessment followed by a site initiation visit (either face to face, or via web) in which the site team will receive protocol specific training in addition to a review of all investigator responsibilities, and expectations of Lumicell. Throughout the conduct of the study Lumicell will conduct intermittent site visits to assure compliance with the protocol and all applicable regulations. During these visits, there will be a source data verification of critical data

LUMICELL CONFIDENTIAL

This document is confidential. Do not disclose or use except as authorized.

points transcribed to the CRF. Data monitoring may also be conducted via central and remote monitoring. At study completion, Lumicell will conduct a study closure visit. This study visit will assure that all site regulatory documentation is present and updated; all data queries are resolved; investigator sign-off/approval of all applicable study data submitted to Lumicell has occurred; and all final disposition instructions from Lumicell have been delivered to the site investigator. Involvement in this study as a participating investigator implies acceptance of the approved protocol, the potential for audits or inspections, including source data verification, by representatives of the FDA, Lumicell (or their affiliates), the institutional review board, or their representatives. The purpose of these audits or inspections is to examine study-related activities and documents to determine whether these activities were conducted and data were recorded, analyzed, and accurately reported in accordance with the protocol, institutional policy, Good Clinical Practices (GCPs), and any applicable regulatory requirements.

All data will be monitored for timeliness of submission, completeness, accuracy, and adherence to protocol requirements.

13.4 Data Safety Monitoring Board

An independent Data Safety Monitoring Board (DSMB) will be established to review the safety of the LUM Imaging System and to review any SAEs that occur during the study. The DSMB will develop and follow a DSMB Charter. The DSMB will be composed of at least 2 oncology specialists (at least one of whom specializes in surgical oncology) and a statistician. The DSMB will be provided with all reports of adverse events including SAEs regardless of investigator causality assessments.

Following the initial meeting, DSMB meetings will occur on a periodic basis in accordance with the DSMB charter. The chairperson of the DSMB will also be immediately provided with the report of any SAE that is judged as possibly, probably, or definitely attributable to treatment with the investigational product. The charter of the DSMB will specify that this committee is charged with providing periodic reports to Lumicell that contain recommendations that include, but are not limited to, (a) continuation of the study, and (b) termination of the study.

14 REGULATORY CONSIDERATIONS

14.1 Protocol review and amendments

This protocol, the proposed informed consent and all forms of subject information related to the study (e.g., advertisements used to recruit subjects) and any other necessary documents must be submitted, reviewed and approved by a properly constituted IRB governing each study location.

Any changes made to the protocol must be mutually agreed upon by Lumicell. Such changes must be submitted as amendments and must be approved by the IRB prior to implementation. Any changes in study conduct must be reported to the IRB. Lumicell will disseminate protocol amendment information to all participating investigators.

All decisions of the IRB concerning the conduct of the study must be made in writing.

In addition, any modifications to the protocol, consent or case report forms will be submitted to the FDA.

14.2 Informed consent

LUMICELL CONFIDENTIAL

This document is confidential. Do not disclose or use except as authorized.

All subjects must be provided a consent form describing this study and providing sufficient information for subjects to make an informed decision about their participation in this study. The formal consent of a subject, using the current IRB approved consent form, must be obtained before any study-related procedures are performed. The consent form must be signed and dated by the subject or the subject's legally authorized representative, and by the person obtaining the consent. The subject must be given a copy of the signed and dated consent document. The original signed copy of the consent document must be retained in the medical record or research file.

14.3 Ethics and Good Clinical Practice (GCP)

This study is to be conducted according to the following considerations, which represent good and sound research practice:

- E6 Good Clinical Practice: Consolidated Guidance
- US Code of Federal Regulations (CFR) governing clinical study conduct and ethical principles that have their origin in the Declaration of Helsinki
 - Title 21 Part 11 – Electronic Records; Electronic Signatures
 - Title 21 Part 50 – Protection of Human Subjects
 - Title 21 Part 54 – Financial Disclosure by Clinical Investigators
 - Title 21 Part 56 – Institutional Review Boards
 - Title 21 Part 812 – Investigational Device Exemptions
- State laws
- Institutional research policies and procedures
- Contractual agreements

It is understood that deviations from the protocol should be avoided, except when necessary to eliminate an immediate hazard to a research subject. In such case, the deviation must be reported to the IRB according to the local reporting policy.

14.4 Study documentation

The investigator and all designees must prepare and maintain adequate and accurate case histories designed to record all observations and other data pertinent to the study for each research subject. This information enables the study to be fully documented and the study data to be subsequently verified.

Original source documents supporting entries in the case report forms include but are not limited to hospital records, clinical charts, laboratory and pharmacy records, recorded data from automated instruments, microfiches, photographic negatives, microfilm or magnetic media, and/or x-rays.

14.4.1 Study Documentation Practices

- a) The investigator must maintain adequate records to enable the conduct of the study to be fully documented
- b) All records, including electronic forms, must be filled out completely. Complete each space or blank. If there is no information to go into a space or blank, then use the symbol "N/A". If an entire section or page of a record is "N/A", it is acceptable to indicate this by drawing one line through the entire section/page and use "N/A" near that line. It is acceptable to check a box marked "N/A" to indicate that a section or an entire page is not applicable. The use of 'White-Out' or similar correction fluid is forbidden.

- c) Use of highlighters on records is acceptable so long as the highlighter color does not obscure the underlying text if the record is copied.
- d) Accuracy is required. Always verify entries are correct and consistent with other information.
- e) Signatures are to be authentic.
- f) Recorded dates are to be the actual dates in which the activities were recorded. Back-dating is forbidden.
- g) If drinks or chemicals are spilled on original records, dry them off to the best of your ability, make an immediate photocopy and make a notation of the event on the copy. Retain the original record except in the event of contamination with a hazardous material.
- h) All forms must be filled out using non-erasable pen and must be legible. The use of blue or black ink is preferred.
- i) Errors must be crossed out with a single line, the correction inserted, and the change initialed and dated by the approved person making the correction. The reason for the correction must be stated.

14.5 Records retention

All study-related documents must be retained for the maximum period required by applicable federal regulations and guidelines, institutional policies or contractual agreement between Lumicell and the participating institution.

15 STATISTICAL CONSIDERATIONS

A full description of the data analysis is included in the Statistical Analysis Plan.

15.1 Analysis Populations

- Safety (SAF) Population: the safety population includes all subjects who received study drug (LUM015).
- Modified Intent To Treat (mITT) population: includes the subjects in SAF, but excluding subjects who are not able to be imaged with the LUM Imaging System. The mITT population will be used as the primary analysis population for the three co-primary efficacy endpoints and efficacy analysis of the secondary endpoints.
- Per-Protocol Population: Includes mITT subjects who complete all study evaluations and are without any major protocol deviations that may impact data collection or efficacy analysis. A sensitivity analysis of the primary and secondary efficacy endpoints will be conducted using the per-protocol analysis set.

15.2 Definition of truth standard for diagnostic performance evaluation (sensitivity and specificity)

We propose to use a hierarchical approach to determine the truth standard as therapeutic shaves were taken only when the LUM imaging system signaled positive for potential residual tumor. The highest truth standard is whether pathology finds cancer in a tissue shave removed from the area that was imaged in the cavity. When a shave does not exist, then whether tumor is found in a re-excision surgery is considered as the truth standard. When neither a shave nor a second surgery exists for a given orientation that was imaged, the margin assessment of that orientation is used as truth standard. **Error! Reference source not found.** shows a schematic for determination of the truth standard.

LUMICELL CONFIDENTIAL

This document is confidential. Do not disclose or use except as authorized.

[figure not shown]

Figure 6: Definition of truth standard to evaluate the LUM Imaging System diagnostic performance.

When the therapeutic shave is not available and the follow-up surgery is performed, only the pathology from the first-time re-excision at the tissue/orientation level will be used for hierarchical sensitivity/specificity evaluation.

The orientation of the tissue removed during a re-excision is typically noted in the pathology report and matches the orientation in which a positive margin was identified from the initial surgery. However, there will be instances in which the orientation of the tissue removed during a re-excision is not specified. In the cases of unclear orientation of the tissue removed during the re-excisions, the orientations with positive margins will be used as positive/negative with cancer as suggested by the pathology of the resected tissue

If a mastectomy is performed as a follow-up surgery and no cancer found in the mastectomy specimen, all the orientation will be considered as cancer negative for truth standard. If mastectomy is performed and cancer is found and no indication of orientations where cancer has been found, the orientation in which a positive margin was identified in the initial lumpectomy will be considered as cancer positive for truth standard unless otherwise noted.

When a therapeutic shave and re-excision are not available for an orientation, the prior margin of the resected tissue of the corresponding orientation will be used as ground inferred truth for evaluation.

Refer to the associated Statistical Analysis Plan (SAP) for additional details.

15.3 Sample Size

The pivotal study will be powered based upon targeting success for the three co-primary endpoints. The efficacy endpoints will be assessed in the patients who undergo LUM imaging (not the 1/10th of subjects randomized to the control arm).

15.3.1 Residual cancer removal

The null hypothesis is that the true percentage of patients in whom at least one LUM-guided shave removed after the SOC procedure contain cancer as confirmed by pathology examination is smaller or equal than 3%:

$$H_0: p \leq 3\%$$

The alternative hypothesis is that the true percentage of patients in whom at least one LUM-guided shave removed after the SOC procedure contain cancer as confirmed by pathology examination is larger than 3%:

$$H_A: p > 3\%$$

where p is the true percentage of patients in whom at least one therapeutic shave removed after the SOC procedure contain cancer as confirmed by pathology examination.

The hypothesis will be tested using an exact Binomial test at a one-sided significance level of 2.5%. The true proportion p will be estimated along with a one-sided 97.5% exact confidence interval.

Lower bound selection for removal of residual cancer endpoint

To choose the success criteria for the proportion of patients who have residual cancer found in at least one LUM-guided shave, we used published results for estimates of local recurrence before and after adjuvant radiation, assuming that most local recurrences are a consequence of unresected cancer during the initial surgery. The meta-analysis conducted on approximately 28,000 patients to support the consensus guideline for margin in 2014 from SSO-ASTRO, reported an overall recurrence rate of 5.3% for patients undergoing lumpectomy and receiving whole breast radiation therapy (including patients with positive and negative margins) [1]. Other investigators have published local recurrence rates for patients with negative margins at 10.2% without a radiation boost, while 6.2% for those with radiation boosts [2]. Based on this data, we estimate that radiation addresses approximately 50% of residual cancer, but not all. Our Phase C results shows a proportion of 26/230 or 11.3% [95% CI: 7.5%-16.1%], supporting the lower bound selection of this endpoint.

Sample size for residual cancer removal

Our preliminary analysis of the Phase C exploratory data indicated that LUM detected residual cavity cancer in 11% of patients (26/230). To power the study, we are using a slightly more conservative assumption of a ~9% true percentage of patients in whom at least one therapeutic shave has cancer confirmed by pathology. With this assumption, enrolling 220 evaluable subjects, a binomial exact test for proportions at a 1-sided significance level of 2.5%, will have 90% power to declare the percentage of patients in whom at least one therapeutic shave has cancer confirmed by pathology to be larger than 3%.

15.3.2 Sensitivity and specificity

The verification of the sensitivity and specificity co-primary endpoints will be a refutation of the null hypotheses

$$H_{01}^S: sen \leq 40\% \text{ against the alternative } H_{11}^S: sen > 40\%$$

$$H_{02}^S: spec \leq 60\% \text{ against the alternative } H_{12}^S: spec > 60\%$$

where *sen* and *spec* represent the true sensitivity and specificity, respectively. These hypotheses will be tested using an exact binomial test for testing proportions in those with a positive ground truth result (sensitivity) and those with a negative ground truth result.

Lower bound selection for sensitivity and specificity endpoints

Data from the Phase C Feasibility Study showed pathology margin assessment sensitivity to predict cancer in the cavity of ~40%. However, this pathology assessment is done several days after the surgery and can lead to second surgeries. Because the LUM Imaging System provides the additional benefit of assessing the cavity in real-time, a lower bound for instrument sensitivity > 40% is proposed as the success criterion for this hypothesis-tested endpoint. We expect the sensitivity to be similar to that observed in the Phase C study of 67% [95% CI: 56%-79%].

The Phase C data shows that at the current specificity performance of 70% [95% CI: 68%-73%], an average of 1.1 additional shaves were removed guided by the LUM Imaging system, accounting for ~10% of all the total resected tissue. We selected a lower bound for specificity of 60% to ensure that similar performance in the pivotal trial is obtain regarding tissue removal. Also, with this lower bound, a Youden Index > 0 will be demonstrated to indicate non-random diagnostic performance.

Sample size for sensitivity

Assuming a sensitivity of 60%, obtaining 70 truth standard positive events, a binomial exact test for proportions at a 1-sided significance level of 2.5%, will have 90% power to declare the lower bound of sensitivity > 40%.

Sample size for specificity

Assuming a specificity of 65%, obtaining 1021 truth standard negative events, a binomial exact test for proportions at a 1-sided significance level of 2.5%, will have 90% power to declare the lower bound of specificity > 60%.

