4.3 Per tissue sensitivity and specificity (co-primary endpoints)

4.3.1 Analysis methods and inpatient correlation

Three separate analyses will be conducted for sensitivity and specificity assessment. The first analysis uses the Binomial estimator and the other two approaches address potential intra patient correlations.

- Binomial estimator: the probability and the confidence interval are estimated according to binomial distribution

LUMICELL CONFIDENTIAL

This document is confidential. Do not disclose or use except as authorized.

- Generalized Estimating Equation (GEE): This method is used to analyze correlated data which is modeled with generalized linear model having binomial link function, and including correlation cluster and matrix information (here within each subject). Procedure Genmod in SAS is used to apply this method (<https://support.sas.com/rnd/app/stat/topics/gee/gee.pdf>). This method with a compound symmetry working correlation structure, will be used to estimate sensitivity and specificity along with a 97.5% lower bounded one-sided confidence interval (CI) (* Tessa S. S. Genders, Sandra Spronk, Theo Stijnen, Ewout W. Steyerberg, Emmanuel Lesaffre, M. G. Myriam Hunink. Methods for Calculating Sensitivity and Specificity of Clustered Data: A Tutorial Radiology: Volume 265 (3):910 (2012)).
- Bootstrapping sampling method: This method is applied to sample the subjects with replacement at the same sample size of mITT for 10,000 rounds. The sampled subjects with corresponding imaging, and standard truth positive and negatives will be used to estimate the sensitivity and specificity. The median sensitivity and specificity will be used as the estimate from bootstrapping method. The 2.5% and 97.5% percentiles will be used as lower and upper bounds, respectively, for 95% confidence intervals.

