4.3.2 Performance goals

The verification of the sensitivity and specificity co-primary endpoints will be a refutation of the null hypotheses

$$H_{01}^s: sen \leq 40\% \text{ against the alternative } H_{11}^s: sen > 40\%$$

$$H_{02}^s: spec \leq 60\% \text{ against the alternative } H_{12}^s: spec > 60\%$$

where *sen* and *spec* represent the true sensitivity and specificity, respectively. The hypotheses involving sensitivity and specificity will be assessed based on the data collected per-tissue level.

These hypotheses will be tested using a one-sided significance level of 2.5%. To account for within-subject correlation, Generalized Estimating Equations (GEE), with a compound symmetry working correlation structure, will be used to estimate sensitivity and specificity along with an equi-tail 95% two-sided confidence interval (CI). The null hypothesis H_{01}^s is rejected if the lower bound of the confidence interval for sensitivity is larger than the performance goal of 40%. Similarly, the null hypothesis H_{02}^s is rejected if the lower bound of the confidence interval for specificity is larger than the performance goal of 60%.

Performance Goals selection for sensitivity and specificity endpoints

Data from the Phase C Feasibility Study showed pathology margin assessment sensitivity to predict cancer in the cavity of ~40%. However, this pathology assessment is done several days after the surgery and can lead to second surgeries. Because the LUM Imaging System provides the additional benefit of assessing the cavity in real-time, a performance goal for instrument sensitivity > 40% is proposed as the success criterion for this hypothesis-tested endpoint. We expect the sensitivity to be similar to that observed in the Phase C study of 69% [95% CI: 56%-80%].

LUMICELL CONFIDENTIAL

This document is confidential. Do not disclose or use except as authorized.

The Phase C data shows that at the current specificity performance of 70% [95% CI: 68%-73%], an average of 1.1 additional shaves were removed guided by the LUM Imaging system, accounting for ~10% of all the total resected tissue. We selected a performance goal for specificity of > 60% to ensure that similar performance in the pivotal trial is obtained regarding tissue removal. Also, with this lower bound, a Youden Index > 0 will be demonstrated to indicate non-random diagnostic performance.

Sample size for testing sensitivity:

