As sensitivity and specificity are estimated at the per tissue level, within subject correlation is considered for the sample size estimation. Intraclass Correlation Coefficient (ICC) was estimated with data from the Feasibility Phase C study. The ICC value was obtained at 0.145 for the full phase data set and at 0.22 for the validation data set which the tumor detection algorithm is same as that used in the pivotal study. We selected ICC at 0.22 for sample size estimation.

The parameters for the simulation is as below:

- True sensitivity is 60%
- Intraclass Correlation Coefficient (ICC) value = 0.22
- Truth standard positive rate 4%
- Performance Goal (PG) = 40%
- 2.5% one-sided significance level
- 70 truth standard positive shaves

Assuming 70 truth standard positive shaves, under the alternative hypothesis, using Generalized Estimating Equation (GEE) model with a compound symmetry working correlation structure, will have >90% power to show that the true sensitivity is > 40%.

Sample size for testing specificity:

The parameters for the simulation is as below:

- True specificity is 65%
- Intraclass Correlation Coefficient (ICC) value = 0.22
- Truth standard negative rate 96%
- Performance Goal (PG) = 60%
- 2.5% one-sided significance level

Under the alternative hypothesis, using Generalized Estimating Equation (GEE) model with a compound symmetry working correlation structure, 1023 truth standard negatives are needed to reach >90% power to show that the true specificity is >60%.

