4.7 Methods for additional analyses

Secondary outcomes involving proportions will be analyzed using methods for Binomial distributions akin to the ones described above. Continuous measurement will be summarized using means and standard deviation and 95% confidence intervals. The percent of people with a specific AE will be reported in prespecified groups. The percent of subjects with adverse events in subjects that have at least one therapeutic shave will be compared with the percent of subjects with adverse events that have no therapeutic shaves using Fisher's exact test or goodness of fit test.

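### The protocol and the SAP name different primary tests for per-tissue sensitivity and specificity, and the protocol's exact binomial test does not hold 2.5% for specificity

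*Protocol*

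**What the plan says.** Protocol 15.3.2 sets the null hypotheses at sensitivity ≤ 40% and specificity ≤ 60% and gives the test: "These hypotheses will be tested using an exact binomial test for testing proportions in those with a positive ground truth result", and likewise for the truth-negatives. Its two sample-size paragraphs (70 positives, 1021 negatives, 90% power each) rest on the same exact test. Nothing there allows for several tissues from one patient.

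SAP 4.3.2 keeps the hypotheses and the unit of analysis: "The hypotheses involving sensitivity and specificity will be assessed based on the data collected per-tissue level". It changes the test: "To account for within-subject correlation, Generalized Estimating Equations (GEE), with a compound symmetry working correlation structure, will be used", and each null is rejected when the lower limit of that interval exceeds the performance goal. The same section reports ICC estimates from the Phase C feasibility study of 0.145 (full data) and 0.22 (validation data, with the pivotal algorithm) and adopts the larger: "We selected ICC at 0.22 for sample size estimation".

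SAP 4.3.1 says "Three separate analyses will be conducted for sensitivity and specificity assessment" and lists binomial, GEE and bootstrap: "The first analysis uses the Binomial estimator and the other two approaches address potential intra patient correlations". None is labelled primary or supportive.

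On precedence, Protocol section 15 opens by pointing to the SAP for the full data analysis, and 15.4.1 says that analyses follow a prespecified SAP. The SAP identifies itself as belonging to CL0007r08, the revision that the note in Protocol 15.3.3 mentions.

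**The concern.** Two current documents attach different tests to the same co-primary hypotheses, and the tests are not interchangeable. A patient contributes up to six orientations, and the sponsor's own Phase C data show that results within a patient are correlated. An exact binomial test on pooled tissues then understates the variance and rejects too often.

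All three co-primaries must succeed, so the worst-case false-success rate of the overall claim is that of its weakest test. A specificity result could also pass under the protocol's wording and fail under the SAP's. A rule that settles which one counts should be in writing before the data are analysed.

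**Working it through.** **Inputs.** Nulls 40% and 60%, alternatives 60% and 65%, 70 positives and 1021 negatives (Protocol 15.3.2). 152 patients for 1021 negatives and 268 patients for 70 positives (Protocol 15.3.3, SAP 4.5). ICC 0.22 and 0.145 (SAP 4.3.2). Upper-tail level 2.5%; the two-sided 5% in Protocol 15.3.4 gives the same upper tail as the SAP's one-sided 2.5%, so the level itself is not in conflict.

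**1. The protocol's figures under independence.** Take the smallest r with P(X ≥ r | null) ≤ 0.025.
- Sensitivity, n = 70: r = 37, actual level 1.99%, power 90.9%.
- Specificity, n = 1021: r = 644, actual level 2.38%, power 90.7%.

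The stated 90% reproduces for both, so the protocol's sizing does assume independent tissues.

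**2. Specificity with correlation.** Negatives per patient m = 1021/152 = 6.72. Design effect = 1 + (m − 1) × ICC.
- ICC 0.22: 1 + 5.72 × 0.22 = 2.26, square root 1.50. The binomial standard error is too small by a factor of 1.5. Approximate level 1 − Φ(1.96/1.50) = 9.6%.
- ICC 0.145: 1 + 5.72 × 0.145 = 1.83, square root 1.35. Approximate level 1 − Φ(1.96/1.35) = 7.4%.

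Beta-binomial simulation of the exact test (200,000 trials per setting, near-equal cluster sizes) at true specificity 60%:

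| Negatives | Patients | ICC | One-sided error |
|---|---|---|---|
| 1021 | 152 | 0.22 | 9.4% |
| 1021 | 152 | 0.145 | 7.1% |
| 1800 (268 × 6.72) | 268 | 0.22 | 9.2% |
| 1021, assuming 4 per patient | 255 | 0.22 | 6.3% |

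More patients do not cure it. GEE with exchangeable correlation and a robust standard error, simulated with 20,000 trials at 6.7 per patient and ICC 0.22, has a level of about 2.6% to 2.9%.

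**3. Sensitivity with correlation.** The documents do not give the number of positives per patient who has any, so it is assumed here. With 70 positives, r = 37 and ICC 0.22:

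| Positives per positive patient | One-sided error |
|---|---|
| 1 | 2.0% |
| 1.25 | 2.5% |
| 1.5 | 2.7% |
| 2 | 3.1% |
| 3 | 4.5% |

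The discreteness of the exact test absorbs light clustering. A rough guide from Phase C: (70/268) × 230 ≈ 60 positives, times 69% sensitivity ≈ 41 detected. If most lie in the 26 patients with a cancer-positive therapeutic shave, that is about 1.6 per patient and an error near 3%.

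**4. Where the two rules part.** At 1021 negatives the binomial test passes at 644/1021 = 63.1%. A correlation-adjusted bound needs about 60% + 1.96 × √(0.24 × 2.26/1021) = 64.5%. At 1800 negatives the figures are 62.3% and 63.4%. An observed specificity between them succeeds under one document and fails under the other.

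**5. Specificity power under the SAP's test.** With ICC 0.22 and 6.72 per patient, GEE power at 65% is 58% to 61% at 1023 negatives and 83% to 84% at 1800; 90% needs about 2,160. The exact binomial test under independence gives 99.1% at 1800 (r = 1122). The SAP's more than 90% at 1023 and more than 99% at the study size are therefore close to what independence gives. At the revised 380 enrolled, with 10/11 in the device arm and no other losses (assumed), there would be 380 × 10/11 × 6.72 ≈ 2,320 negatives and GEE power of about 92%.

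**The case against.** The strongest reply is that the SAP already settles the matter. The protocol's sentence sits under Sample Size, section 15 sends the full analysis to the SAP, and SAP 4.3.2 ties rejection to the GEE interval alone. On that reading the planned test roughly holds its level, and a binomial pass with a GEE fail could be called a success only by disregarding the SAP. Most of this stands, and it lowers the severity. It does not remove the point: the protocol states a test and sizes on it, and no sentence gives the SAP precedence over it.

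Three stronger readings are tempting, and the documents do not support them.

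- A reader might infer that the exact test fails for both endpoints. For sensitivity that depends on a clustering of positives that is not given, and at light clustering the error is at or below 2.5%.
- A reader might take the binomial estimator's first place in SAP 4.3.1 as making it primary. Order is not hierarchy, and only GEE is attached to a rejection rule.
- A reader might extend the point to SAP 4.7 ("Secondary outcomes involving proportions will be analyzed using methods for Binomial distributions akin to the ones described above") and the tissue-level secondary endpoints n and s. Neither has a hypothesis test, and the methods described earlier in the SAP include GEE.

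It is also fair to say that the 9% rests on one reading of the ICC. The SAP's own 1023 negatives at ICC 0.22 does not fit 6.7 per patient, so its simulation may have used another cluster structure. The SAP does not show it. At 4 negatives per patient the error would still be 6.3%.

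**Conclusion.** The point holds as a conflict between the two documents, with a loss of level established for specificity only. The protocol's exact test has a one-sided error of about 9% at ICC 0.22 and about 7% at ICC 0.145, roughly three to four times the nominal 2.5%. For sensitivity it stays near nominal over the plausible range.

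The specificity figures assume beta-binomial clustering, near-equal cluster sizes, 6.7 negatives per patient, and the SAP's ICC applying among negatives, as its specificity simulation sets it. Because GEE probably governs, this is a rule to correct and harmonise; it does not show that the planned analysis is invalid.

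**What to change.** - **Protocol 15.3.2:** replace the exact binomial test with the SAP's rule that each null is rejected when the GEE lower confidence limit exceeds the goal.
- **Protocol 15.3.2 and 15.3.3:** make the sample-size and power statements consistent with that test. Changing the test sentence alone would leave the exact-binomial sizing in place and create a mismatch within the protocol. Restate the specificity power with the ICC and the cluster sizes shown, and give the matching simulation inputs in SAP 4.3.2 and 4.5.
- **SAP 4.3.1:** state that GEE alone decides the two co-primaries and that the binomial and bootstrap analyses are supportive.

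The test change is wording only; the power statement has to be recalculated. Intervals will be wider than the protocol's method gives, and the stated specificity power may be less favourable than the current 90% at 1021 negatives and 99% at the study size.
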